#### *4.5.3 Descriptive/exploratory endpoints*

Descriptive/exploratory endpoints include changes in the following study inclusion until delivery:

- Maternal endpoints
  - Percentage of cases of preeclampsia (see definition in section 3)
  - Percentage of cases of preterm births (see definition in section 3)
  - Percentage of cases of acute caesarean sections
  - Percentage of cases of planned caesarean sections
- Neonatal endpoints
  - Number of cases of neonatal jaundice (see definition in section 3)
- Questionnaires
  - Diabetes Diet-related Quality of Life (DDQOL)
  - Well-being (WHO-5)
  - Health Care Climate Questionnaire (HCCQ)
  - Perceived Competence in Diabetes Scale (PCDS)
  - Diabetes Treatment Satisfaction Questionnaire (DTSQ)
  - Pregnancy Physical Activity Questionnaire (PPAQ)

#### *4.5.4 Endpoints related to intervention and adherence*

- Adherence to intervention (number of no shows for planned visits)
- Number and types of visits (face-to-face, video and telephone)
- Changes in dietary intake with focus on carbohydrate intakes (total intake and meals)
- Adverse events

#### *4.5.5 Endpoints related to hospital costs*

Hospital costs will be analysed for the two study groups (intensive dietary therapy vs. standard care) including costs from referral with GDM to discharge after delivery divided into the categories:

- Outpatient contacts and costs related to the treatment of GDM
- Delivery costs
- Inpatient costs after delivery for mother and offspring separately, including NICU costs
- Total net costs

## 5 Investigational study design

### 5.1 Study design

The INTENSE-GDM trial is a randomised controlled parallel group open-label effectiveness trial aiming to include 214 women with GDM (Figure 1). Participants will attend one consultation with a dietitian in the standard care group and up to 5 consultations with a dietitian in the intensive dietary counselling group. Both groups will receive one end-of-intervention telephone call. Each study visit is described in detail in section 5.4.

#### Study visits

V0: Screening

V1: Baseline visit including one dietary consultation max 2 days after screening (both groups)

[figure not shown]
V2: Follow-up 1 with the dietitian max 2-3 days after V1 (only in the intensive group)

V3: Follow-up 2 with the dietitian a week after V2 (only in the intensive group)

V4: Follow-up 3 with the dietitian only if needed (only in the intensive group)

V5: Follow-up 4 with the dietitian only if needed (only in the intensive group)

V6: Telephone visit 2 weeks before delivery (both groups)

**Figure 1** Study design. Depending on GA at GDM diagnosis and time of delivery the intervention duration will be 5 – 20 weeks. Min. two follow-up consultations are provided in the intensive group.

### 5.2 Randomisation

Participants eligible for inclusion in the study according to the screening will have their baseline measurements collected followed by a randomisation at V1. Participants will be randomised to either an intensive dietary counselling group or a usual dietary care group (control group) in a 1:1 ratio. Randomisation will be performed by the research dietitian using the randomisation module in the software program REDCap. The randomisation list will be made by a researcher/statistician not involved in the trial, who will be the only person to access the randomisation list during the trial. Should this person be unable to continue this function, a new person not involved in the trial will be appointed to store and access the sequence.

## 5.3 Intervention

### 5.3.1 Intensive dietary counselling

Women randomised to the intensive dietary intervention group will receive one initial dietary counselling consultation, and two mandatory follow-up consultations with a dietitian. In addition, participants in this group will be offered 1-2 follow-up consultations if needed (see figure 1).

#### Intervention

- 1 x 60 min initial dietary counselling (in-person)
- 2 x 30 min follow-up dietary consultations (phone/video/in-person according to preference)
- 1-2 x 15-30 min follow-up dietary consultations if needed (phone/video)

The initial dietary counselling includes setting personal dietary goals for behavioural change according to individual challenges with the diet, patient preferences and the overall goal for weight and glycaemic control. Women will be educated in basic carbohydrate counselling. This includes identifying carbohydrates, learning how to count carbohydrates e.g., by calculating the carbohydrate content from food labels, carbohydrate food tables, or apps for smartphones and use of a personalised carbohydrate plan with guiding suggestions for daily intake of carbohydrates at meals based on the personal dietary history. An app from the Danish Diabetes Association (*Diabetes og Kulhydrattælling*®. The Danish Diabetes Association's app, Pragma soft A/S, available in Google Play® and App Store® 12/2014, Free) will be introduced to support calculation of carbohydrates if the patient is able to understand and use this app. In addition, attention concerning carbohydrate quality (dietary fibre intake, and glycaemic index principles) and overall calorie intake will be introduced.

Follow-up consultations will include feedback on postprandial plasma glucose measurements and foods eaten, and adjustments of dietary plan until delivery.

### 5.3.2 Standard dietary care (control)

Women randomised to the standard dietary care group will receive one dietary counselling consultation according to the initial dietary counselling described in section 5.3.1 without any follow-up consultations with a dietitian. Participants are encouraged to follow their dietary plan until delivery.

- 1 x 60 min dietary counselling (in-person)

### 5.3.3 General instructions

[figure not shown]
All study participants will be encouraged to obtain and maintain a moderate-intensity aerobic activity level such as brisk walking during their pregnancy and achieving the best possible sleep. Additionally, all study participants will be instructed to follow their usual care at the Department of Obstetrics at Herlev Hospital and at SDCC if referred to an endocrinologist eventually. The medical doctors at the Department of Obstetrics will assess the need for initiating insulin therapy and referral to an endocrinologist.

### 5.3.4 Adherence

Dietary adherence will be measured by the dietitian using the dietary history method for data collection. A dietary history is a structured interview methods consisting of questions about habitual dietary intake of foods from core food groups, in this study with particular focus on collecting data on carbohydrate sources and estimation of carbohydrate portions sizes (in grams) distributed throughout the day before and after the intervention. Dietary data will be collected at V1 and V6.

## 5.4 Study visits

The following section describes all visits included in the study. An overview of the data collection procedures is presented in table 1. The visits will be conducted by the research dietitians including the principal investigator. Examinations are described in section 7. Windows are allowed for all study visits during the study period. However, we aim to carry out the initial dietary counselling within the first week after referral to Herlev Hospital for both groups, and the first follow-up consultation within the first 2-3 days after the initial dietary counselling in the intensive dietary intervention group. An outline of the protocol is detailed in Figure 2.

**Figure 2** INTENSE-GDM protocol summary

GA, gestational age; GDM, gestational diabetes; HbA1c, haemoglobin A1c; OGTT, oral glucose tolerance test.

### 5.4.1 Screening (V0)

The screening visit (V0) will take place in quiet surroundings at SDCC. After information about the study, and signing of an informed consent, information on medical history (medication, previous and current diseases) will be collected, and in- and exclusion criteria will be assessed by a research dietitian. If the patient fulfils all inclusion criteria and none of the exclusion criteria, the patient will be included in the study. If the patient needs additional time to consider, a new date for a screening visit will be scheduled. If the patient is not eligible for study inclusion the cause of screening failure will be recorded. Patients eligible for inclusion will be registered with an ID code.

#### *5.4.2 Baseline (V1) - both groups*

At the baseline visit (V1) participants will meet with a research dietitian in the clinic at SDCC. The following procedures and assessments will be performed: A clinical examination with measurement of body weight and height; HbA1c after diagnosis will be collected from the patient's medical record; and information about family history and ethnic origin will be collected.

A diet history interview will be performed as part of the dietary counselling focusing on carbohydrate intake before and after diagnosis. The dietitian assesses the diet, and a balanced dietary plan will be prescribed with emphasis on appropriate nutritional intake and distribution especially of carbohydrates, and low glycaemic index diet. Dietary recommendations will be culturally adapted and tailored to the individual.

Randomisation will be performed before the participant is sent home to plan follow-up consultations for women randomised to the intensive dietary group. Questionnaires will be sent electronically through REDCap after the visit.

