The woman will be given time to discuss any questions and will be offered a minimum of 24 hours to consider before signing the informed consent. If the woman decides to participate in the study right away, the woman, and the research dietitian will sign the written informed consent (in Danish or English), and the research dietitian will perform a screening (V0) to assess if the woman is eligible for inclusion in the study. Women eligible for study inclusion will subsequently be offered an initial dietary counselling, performance of baseline measurements, and randomisation (in the mentioned order) (V1) by the research dietitian. Alternatively, the patient will be booked for a visit (V1) within 48 hours after the screening visit. If the woman needs more time to decide if she wants to participate in the study, or has not read the participant information, the research dietitian will schedule for a new meeting after 24 hours.

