## 7 Examinations

All patients found eligible for inclusion in the study will be invited to a first study visit (V1) for collection of baseline measurements according to study specific SOPs. Subsequently, all participants will be randomised to one of the two study groups. All examinations will be performed in the outpatient diabetes clinic at SDCC. Study visits and examinations are described in detail in table 2 below, in the current section and section 5.4.

**Table 2:** Schematic overview of study visits

Visit	V0	V1	V6
Patient-related information			
Informed consent	X		
Assessment of in- and exclusion criteria	X		
Medical history	X		
Dietary history		X	X
Medication use		X	X
Randomisation	X		
Clinical efficacy outcomes			
Insulin use			X
Insulin dose (IE per kg body weight)			X
Time to insulin (days) from study allocation until prescription			X
Diet history interview		X	X
HbA1c		X	X
Body weight and height (height only at V1)		X	X
7-point SMBG		X	X
Questionnaires			
Socio-economic and ethnic characteristics		X	
Well-being (WHO-5)		X	X
Diabetes Diet-Related Quality of Life (DDRQOL)		X	X
Health Care Climate Questionnaire (HCCQ)		X	X
Perceived Competence in Diabetes Scale (PCDS)		X	X
Diabetes Treatment Satisfaction Questionnaire (DTSQ)		X	X
Pregnancy Physical Activity Questionnaire (PPAQ)		X	X

Abbreviations: SMBG, Self-Monitored Blood Glucose; V0, Screening, V1, data collected at baseline; V6, data collected pre-delivery.

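### The baseline questionnaires are sent after open-label randomisation, so the reference value for the patient-reported change scores can already reflect the allocation

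*Protocol*

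**What the plan says.** Section 5.1 describes a "randomised controlled parallel group open-label effectiveness trial". Section 5.4.2 fixes two steps at the end of V1, in this order:

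- Allocation comes first, while the woman is still in the clinic: "Randomisation will be performed before the participant is sent home to plan follow-up consultations for women randomised to the intensive dietary group"
- The six scales reach her only once she has left: "Questionnaires will be sent electronically through REDCap after the visit"

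The section sets no deadline for completing the questionnaires. V2, which only the intensive arm has, is planned 2-3 days after V1 (section 5.1, Figure 1 legend). Section 7.4 also sends the socioeconomic questions electronically after V1.

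Three other sections put baseline collection before allocation:

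- Section 5.2: participants "will have their baseline measurements collected followed by a randomisation at V1".
- Section 5.5: counselling comes first, then "performance of baseline measurements, and randomisation (in the mentioned order) (V1) by the research dietitian".
- Section 7, after describing baseline collection at V1: "Subsequently, all participants will be randomised to one of the two study groups".

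Tables 1 and 2 list all six scales (WHO-5, DDRQOL, HCCQ, PCDS, DTSQ, PPAQ) at V1 and V6. The Table 2 footnote defines the first of these as "V1, data collected at baseline". Section 4.5.3 makes the changes in these scales, from study inclusion to delivery, descriptive/exploratory endpoints. Section 4.4 classes objectives 4 to 7 as descriptive.

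**The concern.** A baseline value is useful in a randomised comparison because allocation cannot have influenced it. Here the woman is randomised openly and, in one arm, leaves with follow-up visits planned. She receives the questionnaires only afterwards. An intensive-arm woman who answers a few days late may already have had V2.

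Satisfaction, autonomy support and perceived competence are what a woman might rate differently once she knows whether she will get further dietitian support. The physical activity questionnaire is less exposed. On a scale where higher is better, anticipation in the intensive arm and disappointment in the control arm both shrink the between-arm difference in change and could hide a real gain. An adverse reaction to the extra visits would have the opposite effect.

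At stake are the patient-reported contrasts under objective 5 and the activity score under objective 6. The primary and secondary endpoints do not use these questionnaires.

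**Working it through.** **Sequence.** The protocol states no figure that needs reproducing; the point follows from the order of procedures.

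| Source | Order given |
|---|---|
| 5.4.2 | Counselling and in-clinic measurements; randomisation; woman goes home; questionnaires sent |
| 5.2, 5.5, 7 | Baseline measurements; then randomisation |
| Tables 1 and 2 | Questionnaires at V1, labelled baseline in Table 2 |
| 4.5.3 | Endpoint is change from study inclusion |
| 5.4.1 | Inclusion takes place at V0 |

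Under 5.4.2 the first questionnaire value is taken neither at inclusion nor before allocation. No visible text places it earlier.

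**Bias.** Let D be the total effect of allocation on the V6 score. Let d be the allocation-induced difference between arms in the V1 score (intensive rise plus control fall), and ρ the slope of V6 on V1. Both scores are scaled to SD 1.

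- V6-only difference: D, bias 0.
- Raw change: D − d, bias −d.
- Baseline-adjusted contrast: about D − ρd, bias about −ρd.

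The documents give neither d nor ρ, so both are assumed over a range:

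| ρ | d (SD) | Raw change: −d | Adjusted: −ρd | V6 only |
|---|---|---|---|---|
| 0.3 | 0.1 | −0.10 | −0.03 | 0.00 |
| 0.3 | 0.3 | −0.30 | −0.09 | 0.00 |
| 0.5 | 0.2 | −0.20 | −0.10 | 0.00 |
| 0.7 | 0.1 | −0.10 | −0.07 | 0.00 |
| 0.7 | 0.3 | −0.30 | −0.21 | 0.00 |

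A simulation (4000 trials per row, true V6 effect 0.30 SD, shift split equally between arms) gave the same values.

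**Scale.** With the planned 214 women, 107 per arm, and every questionnaire returned:

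- SE of the V6-only difference = √(2/107) = 0.137 SD.
- Difference detectable with 80% power = 2.80 × 0.137 = 0.38 SD. This is only a yardstick, because section 4.4 classes these endpoints as descriptive.

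At d = 0.2 and ρ = 0.5, the raw-change bias of 0.20 SD is about one and a half standard errors (0.20/0.137 = 1.46).

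**Precision given up by V6 only.** The SE ratio to an analysis adjusted for a valid baseline is 1/√(1 − ρ²), which is 1.05, 1.15 and 1.40 at ρ = 0.3, 0.5 and 0.7.

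**The case against.** The order of events and the arithmetic are not in dispute. Five arguments can be made against giving the point much weight.

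- **Wording.** Sections 5.2, 5.5 and 7 do not name the questionnaires, and section 7.4 also uses post-visit electronic collection. Baseline measurements may therefore mean the in-clinic items only. This softens the conflict in wording, although the Table 2 label speaks against it. It does not change the timing.
- **Persistence.** The arms stay unblinded, so a fraction k of the reaction may last to V6. Against an effect that excludes the reaction, the biases become (k − 1)d for raw change, (k − ρ)d after adjustment and kd for V6 only. The algebra is right, but it targets a different quantity. For the usual total effect of allocation at V6, raw change is off by −d and the adjusted contrast by about −ρd for any k, and V6 only is unbiased.
- **Unknown size.** The range for d has no basis in the documents. This stands: they show an opportunity for bias, not its size or direction.
- **Low stakes and the unseen SAP.** The endpoints are descriptive, and the estimator may be set in the SAP. The first part limits the weight of the point, but a descriptive label does not make an estimate unbiased. The SAP can choose an estimator; it cannot supply a value that was never collected before randomisation.
- **Cost on site.** Rating care in the clinic, near the dietitian who counselled the woman, may invite socially desirable answers. This is a fair but minor drawback. Before randomisation it cannot differ systematically by arm.

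**Conclusion.** The concern holds. As the protocol stands, the questionnaire values labelled baseline are collected after open-label allocation, with no completion deadline, and can follow the first contact that only one arm receives. Change scores built on them are biased by −d, or about −ρd after adjustment. Under the assumed ranges this is −0.10 to −0.30 SD and −0.03 to −0.21 SD respectively.

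The sequence is certain. The size rests entirely on the assumed d and ρ, and the sign would reverse if the extra visits were received badly. The damage is confined to descriptive endpoints: the primary and secondary endpoints and the sample size calculation are untouched. The change is worth making because it is cheap and the loss cannot be repaired afterwards.

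**What to change.** - Have the six questionnaires completed on site at V1, after counselling and before randomisation is run in REDCap. The order in section 5.5 already allows this, and counselling is not delayed.
- Record completion time relative to randomisation and to V2.
- If a woman cannot finish in time, randomise her as planned and flag her questionnaire as post-randomisation, not as baseline.
- For women already randomised under the present order, compare V6 scores between arms. Do not use the first questionnaire as change reference or covariate.
- Editorial: Table 2, as extracted, marks randomisation at V0, while sections 5.2, 5.4.2 and 5.5 place it at V1. Reconcile these. The questionnaires follow randomisation under either placement.

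The cost is a changed REDCap trigger, one table cell, and on-site time for six instruments in a visit that already holds a 60-minute consultation. It takes longer where an interpreter is needed. For women already randomised, the V6-only comparison also carries the loss of precision shown above.

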#### *5.4.3 Intervention - intensive dietary group (V2)*

V2 is a mandatory follow-up visit with the dietitian either in person or remote as telemedicine based on the participant's preference. The visit will take place  $\pm 2-3$  days after the initial dietary counselling (V1). Focus will be on dietary adherence, carbohydrate distribution and amounts of carbohydrates eaten at each meal in relation to 7-point SMBG measurements in this dietary consultation.

#### *5.4.4 Intervention - intensive dietary group (V3)*

V3 is a mandatory follow-up visit with the dietitian either in person or remote as telemedicine based on the participant's preference. The visit will take place  $\pm 7$  days after V2. Focus will be on dietary adherence, in relation to 7-point SMBG measurements. Evaluation of the need for a dietary follow-up visit.

#### *5.4.5 Intervention - intensive dietary group (V4)*

Optional follow-up telemedicine consultation with the dietitian. The visit can take place up to 3 weeks before delivery.

#### *5.4.6 Intervention - intensive dietary group (V5)*

Optional follow-up telemedicine consultation with the dietitian. The visit can take place up to 3 weeks before delivery.

#### *5.4.7 Pre-delivery visit (V6) - both groups*

A telephone visit will be carried out 1-2 weeks before the planned delivery with both groups. A diet history interview will be performed focusing on the carbohydrate intake during the intervention period. Obstetric history, changes in medication, HbA1c, body weight and 7-point SMGB measurements registered in the participant's medical record will be recorded in REDCap. Questionnaires will be sent electronically through REDCap after the telephone visit.

**Table 1. Data collection procedures in the INTENSE-GDM Trial**

Variable	Measurement	Participant	Screening V0	Baseline V1	Pre-delivery V6	Post-delivery No visit
Ethnicity and socio-economic status	Self-constructed questions	W		•		
Medical history	EMR	W	•	•		
Dietary history	Personal interview	W		•	•	
Alcohol, sleep, and smoking	Self-constructed questions	W		•	•	
Obstetric history	EMR	W		•	•	•
Medication	EMR	W		•	•	
Glucose control	HbA1c	W		•	•	
	7-point SMGB	W		•	•	
	Neonatal hypoglycaemia	N				•
	Admission to NICU	W, N				•
Anthropometry	Height, BW, BMI	W		•	•	
	Delivery weight (EMR)	N				•
	LGA (EMR)	N				•
	SGA (EMR)	N				•
	Macrosomia (EMR)	N				•
Delivery complications	Preterm birth (EMR)	W				•
	Preeclampsia (EMR)	W				•
	Caesarean section (EMR)	W				•
	Jaundice (EMR)	N				•
Well-being	The WHO-Five Wellbeing Index (WHO-5)(33)	W		•	•	
Diet-Related Quality of Life	Diabetes Diet-Related Quality of Life (DDRQOL) (34)	W		•	•	
Autonomy support	Health Care Climate Questionnaire (HCCQ) (35)	W		•	•	
Perceived competences	Perceived Competence in Diabetes Scale (PCDS) (35)	W		•	•	
Treatment satisfaction	Diabetes Treatment Satisfaction Questionnaire (DTSQ) (36, 37)	W		•	•	
Physical activity	Pregnancy Physical Activity Questionnaire (PPAQ) (38)	W		•	•	
Adherence	EMR data	W				•
Hospital costs	EMR and registry data	W, N				•
Safety	Adverse events	W			•	•

BMI, Body Mass Index; BW, Body weight; EMR, Electronic Medical Record; HbA1c, Haemoglobin A1c; W, Woman with GDM; N, neonate delivered by women with GDM in the study; NICU, neonatal intensive care unit.

## 5.5 Recruitment and informed consent

We plan to recruit at 214 women with GDM from the Department of Obstetrics at Herlev-Gentofte Hospital. Written informed consent will be obtained either in paper format or digitally using REDCap prior to entry into the study.

Participants will be recruited when they are newly diagnosed with GDM and referred to the Department of Obstetrics at Herlev Hospital for GDM management. A written participant information in Danish and English will be sent together with the brochure "*Forsøgspersoners rettigheder i et sundhedsvidenskabeligt forskningsprojekt*" through E-Boks together with the invitation to the initial consultation with a dietitian (standard procedure). The right to bring a relative is mentioned in the written information. Women are encouraged to bring their partner. There will be allocated plenty of time for the oral study information at the first appointment with one of the research dietitians (who also perform the routine dietitian visits with all women with GDM). The research dietitian will start by asking the woman if she has read the participant information and if she is still interested in oral information about the clinical trial. If she has read the information and is still interested, the research dietitian will provide an oral information (either in Danish or English or together with an interpreter) including information about study objectives, significance, content, and requirements including risks implications and principles for randomisation with allocation to one of two groups. In particular, the woman will be informed about: 1) the possibility of withdrawing from the study at any time without giving any reason; 2) how personal health-related data will be collected and used and processed in accordance with the data protection legislation in the study; and 3) that all personal and health-related data will be anonymised.

The woman will be given time to discuss any questions and will be offered a minimum of 24 hours to consider before signing the informed consent. If the woman decides to participate in the study right away, the woman, and the research dietitian will sign the written informed consent (in Danish or English), and the research dietitian will perform a screening (V0) to assess if the woman is eligible for inclusion in the study. Women eligible for study inclusion will subsequently be offered an initial dietary counselling, performance of baseline measurements, and randomisation (in the mentioned order) (V1) by the research dietitian. Alternatively, the patient will be booked for a visit (V1) within 48 hours after the screening visit. If the woman needs more time to decide if she wants to participate in the study, or has not read the participant information, the research dietitian will schedule for a new meeting after 24 hours.

